15.1.2 Ethical Conduct of the Study

This research will be carried out in accordance with the protocol, US Code of Federal Regulations, 21 CFR Parts 50, 56, and 312, the ethical principles set forth in the Declaration of Helsinki, GCP, and the ICH harmonized tripartite guideline regarding GCP (E6 Consolidated Guidance, April 1996).

15.1.3 Subject Information and Consent

The purpose of the study, the procedures to be carried out and the potential hazards will be described to the subjects in non-technical terms. Subjects will be required to read, sign and date an ICF summarizing the discussion prior to screening, and will be assured that they may withdraw from the study at any time without jeopardizing their medical care.

Subjects will be given a copy of their signed ICF.

15.2 Termination of the Study

Celerion reserves the right to terminate the study in the interest of subject welfare.

Sponsor reserves the right to suspend or terminate the study at any time.

15.3 Data Quality Assurance

Standard operating procedures are available for all activities performed at Celerion relevant to the quality of this study. Designated personnel of Celerion will be responsible for implementing and maintaining quality assurance (QA) and quality control systems to ensure that the study is conducted, and that data are generated, documented and reported in compliance with the study protocol, GCP and GLP requirements as well as applicable regulatory requirements and local laws, rules and regulations relating to the conduct of the clinical study.

The Clinical Study Report will be audited by the QA department and the QA audit certificate will be included in the study report.

All clinical data will undergo a 100% quality control check prior to clinical database lock. Edit checks are then performed for appropriate databases as a validation routine using SAS® or comparable statistical program to check for missing data, data inconsistencies, data ranges, etc. Corrections are made prior to database lock.

15.4 Direct Access to Source Data/Documents

Celerion will ensure that the Sponsor, IRB and inspection by domestic and foreign regulatory authorities will have direct access to all study-related sites, source data/documents, and reports for the purpose of monitoring and auditing (ICH[E6] 5.1.2 & 6.10). In the event that other study-related monitoring should be done by other parties, they will be required to sign a confidentiality agreement prior to any monitoring and auditing.

15.5 Drug Supplies, Packaging and Labeling

The Sponsor will supply sufficient quantities of LOXO-292 capsules to allow completion of this study. Celerion will provide sufficient quantities of omeprazole delayed-release capsules to allow completion of the study. The lot numbers and expiration dates (where available) of the study drugs supplied will be recorded in the final report.

Records will be made of the receipt and dispensing of the study drugs supplied. At the conclusion of the study, any unused study drugs will be retained by Celerion, returned to the Sponsor or designee, or destroyed, as per Sponsor instructions. Any remaining supplies that were purchased by Celerion will be destroyed. If no supplies remain, this fact will be documented in the pharmacy product accountability records.

15.6 Data Handling and Record Keeping

Celerion standard CRFs will be supplied. CRFs are printed off directly from the database. Each CRF is reviewed and signed by the PI.

All raw data generated in connection with this study, together with the original copy of the final report, will be retained by Celerion until at least 5 years after the last approval of a marketing application in an ICH region and until there are no pending or contemplated marketing applications in an ICH region or at least 5 years have elapsed since the formal discontinuation of clinical development of the investigational product. These documents should be retained for a longer period however if required by the applicable regulatory requirements or by an agreement with the sponsor. It is the responsibility of the Sponsor to inform the PI/Institution as to when these documents no longer need to be retained.

15.7 Report Format

According to the ICH Harmonized Tripartite Guideline (Organization of the Common Technical Document for the Registration of Pharmaceuticals for Human Use M4 and the ICH M2 Expert Working Group), the final report will be written according to the ICH E3 Guideline (Structure and Content of Clinical Study Reports).

15.8 Publication Policy

All unpublished information given to Celerion by the Sponsor shall not be published or disclosed to a third party without the prior written consent of the Sponsor.

The data generated by this study are considered confidential information and the property of the Sponsor. This confidential information may be published only in collaboration with participating personnel from the Sponsor or upon Sponsor's written consent to publish the article.

## 1. INTRODUCTION

The following statistical analysis plan (SAP) provides the framework for the summarization of the data from study LOXO-RET-18015. The SAP may change due to unforeseen circumstances. Any changes made from the planned analysis within the protocol or after the locking of the database will be documented in the clinical study report (CSR). The section referred to as Table Shells within this SAP describes the traceability of the tables, figures, and listings (TFLs) back to the data. Note that the header for this page will be the one used for the main body of the CSR.

Any additional exploratory analyses not addressed within this SAP and/or driven by the data, or requested by Loxo Oncology, Inc., will be considered out of scope and will be described in the CSR as needed.

## 2. OBJECTIVES AND ENDPOINTS

### 2.1 Objectives

#### Primary:

1. To assess the effect of food on the pharmacokinetics (PK) of LOXO-292 after a high fat meal in healthy adult subjects.
2. To assess the effect of a gastric pH change on the PK of LOXO-292 after multiple doses of a proton pump inhibitor (PPI), omeprazole, under fasted and fed conditions in healthy adult subjects.

#### Secondary:

To determine the safety and tolerability of a single dose of LOXO-292 with and without food, alone or in the presence of a PPI (omeprazole) in healthy adult subjects.

### 2.2 Endpoints

#### Pharmacokinetics:

The PK endpoints will include AUC0-t, AUC0-inf, AUC%extrap, Cmax, Tmax, Kel, CL/F, and t1/2 for LOXO-292 administered with and without food, and with and without PPI (omeprazole).

#### Safety:

Safety endpoints will include 12-lead electrocardiograms (ECGs), physical examinations, vital signs, clinical laboratory tests, and adverse events (AEs).

### 3. STUDY DESIGN

This is an open label, randomized, 4-treatment, crossover study.

CCI [REDACTED] healthy, adult male and female subjects (women of non-childbearing potential only) were enrolled. Every attempt were made to enroll at least 3 subjects of each sex in the study.

Screening of subjects occurred within 28 days prior to the first dosing.

Subjects were randomized to one of four treatment sequences: ABCD, ABDC, BACD, and BADC. Every attempt was made to include the same number of females in each sequence and the same number of males in each sequence.

On Day 1 of Periods 1 and 2, a single oral dose of LOXO-292 was administered under fasted or fed conditions, according to the randomization schedule, followed by PK sampling for 168 hours.

In Periods 3 and 4, multiple oral doses of omeprazole were administered once daily from Day -4 of Period 3 until Day 7 of Period 4, inclusive (for a total of 18 consecutive days) with a single oral dose of LOXO-292 coadministered on Day 1 of each period under fasted or fed conditions, according to the randomization schedule. Pharmacokinetic sampling for LOXO-292 was taken for 168 hours following LOXO-292 dosing on Day 1 in each period.

There was a washout period of 7 days between LOXO-292 dose in Period 1 and LOXO-292 dose in Period 2 and between the LOXO-292 dose in Period 2 and the first dose of omeprazole in Period 3. There was no washout between Periods 3 and 4 omeprazole doses although the LOXO-292 doses will be separated by a 7-day washout.

Safety was monitored throughout the study by repeated clinical and laboratory evaluations.

Subjects were permitted to be replaced at the discretion of the Sponsor, but no subjects were replaced on this study.

Subjects were housed throughout the study beginning on Day -1 of Period 1, at the time indicated by the CRU, until after completion of the 168-hour blood draw and/or study procedures in Period 4. At all times, a subject may have been required to remain at the CRU for longer at the discretion of the Principal Investigator (PI) or designee.

The CRU made every attempt to contact all subjects who received at least 1 dose of study drug (including subjects who terminated the study early) using their standard procedures (i.e., phone call or other method of contact) approximately 7 days after the

last study drug administration (LOXO-292 or omeprazole, whichever came last) to determine if any AE had occurred since the last study visit.

#### **4. ANALYSIS POPULATIONS**

##### **4.1 Analysis Populations**

###### **Safety Population**

All subjects who received at least one dose of LOXO-292 will be included in the safety evaluations.

###### **Pharmacokinetic Population**

Samples from all subjects will be assayed even if the subjects do not complete the study. All subjects who comply sufficiently with the protocol and display an evaluable PK profile (e.g., exposure to treatment, availability of measurements and absence of major protocol violations) will be included in the statistical analyses.

Data for each subject will be included in the summary statistics and statistical comparisons of PK parameters with the exceptions described as follows:

- Data from subjects who experience emesis at or before 2 times median Tmax for the given treatment during the PK sampling period time course of the study for LOXO-292 will be excluded from the summary statistics for the given treatment and from the statistical comparison of PK parameters.
- Data from subjects who significantly violate a protocol inclusion or exclusion criteria, deviate significantly from the protocol, or have unavailable or incomplete data which may influence the PK analysis will be excluded from the PK Population.

Any subject or data excluded from the analysis will be identified, along with their reason for exclusion, in the CSR.

##### **4.2 Preliminary Data and Interim Analysis**

No interim analysis is planned for this study.

#### **5. TREATMENT DESCRIPTIONS**

LOXO-292 was supplied as 80 mg capsules.

Omeprazole was supplied as 40 mg delayed-release capsules.

All study drugs were administered orally with approximately 240 mL of water.

Subjects were instructed not to crush, split, or chew the study drugs.

Treatments A and B were dosed in Periods 1 and 2 and Treatments C and D were dosed in Periods 3 and 4 according to the randomization schedule. Treatments are described as follows:

Periods 1 and 2:

**All Subjects** CCI

Treatment	Short Description (text, tables headers, figures, listings, SAS output)	Abbreviated Description
A	160 mg LOXO-292 fasted	160 mg LOXO-292 (2 x 80 mg capsules) at Hour 0 on Day 1 administered under fasting conditions.
B	160 mg LOXO-292 fed	160 mg LOXO-292 (2 x 80 mg capsules) at Hour 0 on Day 1 administered 30 minutes after the start of a high fat breakfast.

Periods 3 and 4:

Subjects were administered 40 mg of omeprazole (1 x 40 mg capsule) every 24 hours (within  $\pm$  1 hour of dosing time on Day -4 of Period 3) from Day -4 of Period 3 to Day 7 of Period 4, inclusive.

**All Subjects** CCI

Treatment	Short Description (text, tables headers, figures, listings, SAS output)	Abbreviated Description
C	Omeprazole + 160 mg LOXO-292 fasted	Multiple daily doses of 40 mg omeprazole (1 x 40 mg capsule) from Day 1 to Day 7 with 160 mg LOXO-292 (2 x 80 mg capsules) coadministered at Hour 0 on Day 1 under fasting conditions.
D	Omeprazole + 160 mg LOXO-292 fed	Multiple daily doses of 40 mg omeprazole (1 x 40 mg capsule) from Day 1 to Day 7 with 160 mg LOXO-292 (2 x 80 mg capsules) coadministered at Hour 0 on Day 1, 30 minutes after the start of a high fat

		breakfast.
--	--	------------

For AEs, an additional treatment was added to account for the 4 days of omeprazole alone from Day -4 to Day -1 of Period 3.

Treatment	Short Description (text, tables headers, figures, listings, SAS output)	Abbreviated Description
OMP Alone	Omeprazole alone	Multiple daily doses of 40 mg omeprazole (1 x 40 mg capsule) from Day -4 to Day -1 of Period 3.

## 6. PHARMACOKINETIC ANALYSIS

### 6.1 Measurements and Collection Schedule

Blood samples for PK assessment of LOXO-292 were taken at the following time points on Day 1 of each period: at predose and 0.25, 0.5, 0.75, 1, 1.5, 2, 2.5, 3, 4, 6, 8, 12, 24, 48, 72, 96, 120, 144, and 168 hours postdose.

The 168-hour blood draw in Period 1 was the same as the predose blood draw in Period 2. The 168-hour blood draw in Period 3 was the same as the predose blood draw in Period 4.

All concentration data will be included in the calculation of the individual PK parameters, the individual concentration-time plots (based on actual sample times), and in the mean concentration-time plots (based on nominal sample times). However, if there were any significant deviations from nominal sample times, some concentration data may be excluded from mean concentration-time plots and/or additional concentration-time plots of the mean data may be provided. All deviations and excluded data will be provided and discussed in the CSR.

### 6.2 Bioanalytical Method for LOXO-292

Plasma concentrations of LOXO-292 were determined using a liquid chromatography-tandem mass spectrometry (LC-MS/MS) method validated with respect to accuracy, precision, linearity, sensitivity, and specificity at Alturas Analytics, Inc. (Moscow, Idaho, USA). The analytical range (lower limit of quantitation [LLOQ] – upper limit of quantitation [ULOQ]) for LOXO-292 is 1 – 1000 ng/mL. Samples that contain concentrations greater than 1000 ng/mL may have been diluted up to 51-fold, if necessary, to be within the quantification range.

### 6.3 Investigational Product and PK Analyte Information of LOXO-292

LOXO-292 has a molecular weight of approximately 500 g/mol. LOXO-292 was supplied as a powder-in-capsule containing 80 mg of drug substance (freebase) and as a simple blend with excipients in a hard gelatin capsule.

### 6.4 Pharmacokinetic Concentrations

Plasma concentrations of LOXO-292 as determined at the collection times and per the bioanalytical method described in Section 6.1 and Section 6.2, respectively, will be used for the calculation of the plasma LOXO-292 PK parameters.

### 6.5 Noncompartmental Pharmacokinetic Analysis and Parameter Calculation for LOXO-292

The appropriate noncompartmental PK parameters will be calculated from the plasma LOXO-292 concentration-time data using Phoenix® WinNonlin® Version 7.0 or higher. Actual sample times will be used in the calculations of the PK parameters. All PK parameters included in the protocol are listed in Table 6.1 below, and are defined as appropriate for study design.

**Table 6.1. Noncompartmental Pharmacokinetic Parameters to be Calculated for LOXO-292**

Label to be Used in the Text, Tables and Figures	Definition	Method of Determination
AUC0-t	Area under the concentration-time curve from time 0 to the time of the last observed non-zero concentration	Calculated using the Linear Trapezoidal with Linear Interpolation Method
AUC0-inf	Area under the concentration-time curve from time 0 extrapolated to infinity	Calculated as AUC0-t + (Clast/Kel) where Clast is the last observed/measured concentration
AUC%extrap	Percent of AUC0-inf extrapolated	Calculated as (1-AUC0-t/AUC0-inf)*100
Cmax	Maximum observed concentration	Taken directly from bioanalytical data
Tmax	The time to reach Cmax. If the maximum value occurs at more than one time point, Tmax is defined as the first time point with this value	Taken from clinical database as the difference in the time of administration and the time of the blood draw which is associated with the Cmax.

Label to be Used in the Text, Tables and Figures	Definition	Method of Determination
CL/F	Apparent total plasma clearance after oral (extravascular) administration	Calculated as Dose/(AUC 0-inf )
Kel	Apparent terminal elimination rate constant; represents the fraction of drug eliminated per unit time	Calculated as the negative of the slope of a linear regression of the log(concentration)-time for all concentrations > LLOQ
t 1/2	Apparent first-order terminal elimination half-life	Calculated as 0.693/Kel

Pharmacokinetic parameters will not be calculated for subjects with fewer than 3 consecutive postdose time points with quantifiable concentrations. Subjects for whom there are insufficient data to calculate the PK parameters will be included in the concentration tables only and excluded from the statistical analysis.

For the calculation of the PK parameters, plasma concentrations below the limit of quantitation (BLQ) prior to the first quantifiable concentration will be set to 0 and plasma concentrations BLQ after the first quantifiable concentration will be treated as missing.

The Kel will be determined using linear regressions composed of at least 3 data points. The Kel will not be assigned if 1) the terminal elimination phase is not apparent, 2) if Tmax is one of the 3 last data points, or 3) if the R^2 value is less than 0.75. In cases where the Kel interval is not assigned, the values of t1/2, AUC0-inf, and CL/F are considered not calculable and will not be reported. Wherever the resulting t1/2 is more than half as long as the sampling interval, the Kel values and associated parameters (t1/2, AUC0-inf, AUC%extrap, and CL/F) may not be presented as judged appropriate and in accordance with Celerion SOPs.

If predose measurable concentrations were to occur, the following procedure will be used: if the predose concentration is less than or equal to 5% of Cmax for that subject period, the subject's data will be included in all PK measurements and calculations without any adjustments. If the predose value is greater than 5% of Cmax, the subject will be excluded from the PK analysis for that period only.

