LOXO-292 has been given orally and intravenously to mice, rats, dogs, minipigs, and monkey. LOXO-292 was absorbed and bioavailable in all species tested. Solubility studies and pharmacokinetic studies suggest that the pharmacokinetic exposure of LOXO-292 may be reduced by proton pump inhibitors and other antacids. LOXO-292 appears to be metabolized primarily by CYP3A4, but at therapeutically relevant exposures, it is not anticipated to inhibit or induce drug-metabolizing enzymes. LOXO-292 is also a substrate for Breast Cancer Resistance Protein transporter.

Refer to the Investigator's Brochure for detailed background information on LOXO-292 [[Investigator's Brochure 2018](#)].

Clinical

LOXO-292 is currently being studied in an ongoing global Phase 1 first in human Study LOXO-RET-17001 in patients with advanced solid tumors including RET fusion-positive NSCLC, RET-mutant MTC, and other tumors with increased RET activity. The starting dose of LOXO-292 was 20 mg once daily. As of a January 5, 2018 data cut-off date, safety data was available from 57 patients with 160 mg BID as the highest dose administered. As of the January 5, 2018, no dose-limiting toxicities have been reported. TEAEs occurring in $\geq 10\%$ of patients were: fatigue (16%), diarrhea (16%), and dyspnea (12%). The majority of TEAEs were Grades 1 or 2 and no \geq Grade 3 TEAEs were related to study drug. Three subjects have died during the study, and no deaths have been attributed to study drug..

Loxo Oncology has also initiated 3 IRB-approved, FDA-allowed single patient protocols (LOXO-RET-17002, LOXO-RET-17003, and LOXO-RET-17004) to provide access to LOXO-292 for patients with clinical need not meeting eligibility criteria for the ongoing clinical studies. As of January 5, 2018, no TEAEs have been attributed to study drug for these patients.

As of February 9, 2018, PK data were available from patients (from the LOXO-RET-17001 study). LOXO-292 is absorbed after oral administration with a time to maximum concentration (Tmax) of approximately 2 hours. Although the pharmacokinetic sampling of LOXO-292 was not long enough to adequately characterize AUC0-inf, the half-life was estimated to be at least 12 hours or longer. Low concentrations of LOXO-292 were recovered as unchanged drug in urine indicating that the kidney contributes to overall clearance.

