13.3.2 Plasma Pharmacokinetic Parameters

PK parameters for plasma LOXO-292 will be calculated as follows, as appropriate:

AUC0-t:	The area under the concentration-time curve, from time 0 to the last observed non-zero concentration, as calculated by the linear trapezoidal method.
AUC0-inf:	The area under the concentration-time curve from time 0 extrapolated to infinity. AUC0-inf is calculated as the sum of AUC0-t plus the ratio of the last measurable plasma concentration to the elimination rate constant.
AUC%extrap:	Percent of AUC0-inf extrapolated, represented as $(1 - AUC0-t/AUC0-inf) * 100$.
Cmax:	Maximum observed concentration.
CL/F:	Apparent total plasma clearance after oral (extravascular) administration, calculated as Dose/AUC0-inf.
Tmax:	Time to reach Cmax. If the maximum value occurs at more than one time point, Tmax is defined as the first time point with this value.
Kel:	Apparent first-order terminal elimination rate constant calculated from a semi-log plot of the plasma concentration versus time curve. The parameter will be calculated by linear least-squares regression analysis using the maximum number of points in the terminal log-linear phase (e.g., three or more non-zero plasma concentrations).
t _{1/2} :	Apparent first-order terminal elimination half-life will be calculated as $0.693/Kel$.

No value for Kel, AUC0-inf, CL/F, or t_{1/2} will be reported for cases that do not exhibit a terminal log-linear phase in the concentration-time profile.

No PK parameters will be calculated for subjects with 2 or fewer consecutive time points with detectable concentrations.

Individual and mean plasma concentration time curves (both linear and log-linear) will be included in the final report.

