# 8. SUMMARY OF CHANGES FROM PROTOCOL-PLANNED ANALYSIS

The analyses described in this SAP are aligned with those analyses described in the protocol.

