**Notes for Generating the Actual Table:**

Presentation of Data:

- Subject number to be presented as follow: XXX-XXX
- PK Parameters will be presented in the following order: AUC0-t <unit>, AUC0-inf <unit>, AUC%extrap <unit>, Cmax <unit>, Tmax <unit>, Kel <unit>, t1/2 <unit>, and CL/F <unit>
- n will be presented as an integer (with no decimal);
- Parameter values for exposure-based parameters (i.e. AUCs, AUC%extrap, Cmax, and CL/F) will be presented with, at maximum, the precision of the bioanalytical data, and, at minimum, 3 significant figures (to be determined by the PKist once the bioanalytical data are received).
  - Summary statistics for exposure parameters will be presented as: Mean, Median, and Geom Mean +1; SD and SEM +2, Min and Max +0 with respect to the number of significant figures.
- Values for time-based parameters (i.e. Tmax, and t1/2) will be presented with 2 decimals.
  - Summary statistics for time-based parameters will be presented as: Mean, Median, and Geom Mean +1; SD and SEM +2, Min and Max +0 with respect to the number of decimals.
- Values for rate constants (i.e. Kel) will be presented with 3 significant figures.
  - Summary statistics for Kel will be presented as: Mean, Median, and Geom Mean +1; SD and SEM +2, Min and Max +0 with respect to the number of significant figures.
- CV% and Geom CV% for all parameters will be presented with 1 decimal

Program: /CAXXXX/sas\_prg/plsas/pk-tables.sas  
Program: /CAXXXX/sas\_prg/plsas/adam\_pkparam.sas

DDMMYYYY HH:MM  
DDMMYYYY HH:MM

Table 14.2.1.9 will be in the following format:

Table 14.2.1.9 Intervals (Hours) Used for Determination of Plasma LOXO-292 Kel Values Following Administration of 160 mg LOXO-292 Fasted (Treatment A), Administration of 160 mg LOXO-292 Fed (Treatment B), Coadministration of Multiple Dose Omeprazole + 160 mg LOXO-292 Fasted (Treatment C), and Coadministration of Multiple Dose Omeprazole + 160 mg LOXO-292 Fed (Treatment D) (Pharmacokinetic Population)

Subject Number	Treatment Sequence	Treatment A			Treatment B		
		Interval	R2	n	Interval	R2	n
XXX-XXX	XX	XX.X – XX.X	X.XXX	X	XX.X – XX.X	X.XXX	X
XXX-XXX	XX	XX.X – XX.X	X.XXX	X	XX.X – XX.X	X.XXX	X
XXX-XXX	XX	XX.X – XX.X	X.XXX	X	XX.X – XX.X	X.XXX	X
XXX-XXX	XX	XX.X – XX.X	X.XXX	X	XX.X – XX.X	X.XXX	X
XXX-XXX	XX	XX.X – XX.X	X.XXX	X	XX.X – XX.X	X.XXX	X
XXX-XXX	XX	XX.X – XX.X	X.XXX	X	XX.X – XX.X	X.XXX	X

Treatment A: 160 mg LOXO-292 (2 x 80 mg capsules) at Hour 0 on Day 1 administered under fasting conditions.

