Treatment B: 160 mg LOXO-292 (2 x 80 mg capsules) at Hour 0 on Day 1 administered 30 minutes after the start of a high fat breakfast.

Treatment C: Multiple daily doses of 40 mg omeprazole (1 x 40 mg capsule) from Day 1 to Day 7 with 160 mg LOXO-292 (2 x 80 mg capsules) coadministered at Hour 0 on Day 1 under fasting conditions.

Treatment D: Multiple daily doses of 40 mg omeprazole (1 x 40 mg capsule) from Day 1 to Day 7 with 160 mg LOXO-292 (2 x 80 mg capsules) coadministered at Hour 0 on Day 1, 30 minutes after the start of a high fat breakfast.

R2 = Coefficient of determination

n = Number of points used in Kel calculation

. = Kel value not reportable.

Loxo Oncology, Inc.  
LOXO-292, LOXO-RET-18015  
Celerion, Clinical Study Report No. CA24336

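### SAP Table 6.1 fits Kel to every quantifiable concentration, whereas Protocol 13.3.2 and the SAP's own Kel interval call for a terminal-phase fit

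*SAP*

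**What the plan says.** **SAP Table 6.1, Kel row.** The definition column reads "Apparent terminal elimination rate constant; represents the fraction of drug eliminated per unit time". The method column reads "Calculated as the negative of the slope of a linear regression of the log(concentration)-time for all concentrations > LLOQ".

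**Protocol 13.3.2.** Kel comes from least-squares regression on the semi-log plot, "using the maximum number of points in the terminal log-linear phase". Without such a phase, Kel, AUC0-inf, CL/F and t1/2 are not reported.

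**SAP 6.5, text after Table 6.1.** At least 3 points are required. Kel is withheld if no terminal phase is apparent, if Tmax is among the last 3 points, or if R² is below 0.75. The sentence that follows opens "In cases where the Kel interval is not assigned" and makes t1/2, AUC0-inf and CL/F not calculable in that event.

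**SAP Table 14.2.1.9 shell.** Its title begins "Intervals (Hours) Used for Determination of Plasma LOXO-292 Kel Values". It prints an interval, R² and a count for each profile, with the footnote "n = Number of points used in Kel calculation".

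**SAP section 8.** "The analyses described in this SAP are aligned with those analyses described in the protocol". No change to Kel is listed.

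**The concern.** The Table 6.1 cell and Protocol 13.3.2 specify different sets of points. The cell is also at odds with its own row, which defines a terminal constant, and with an output table that would have little purpose if every quantifiable point were always used. The conditions in SAP 6.5 decide whether Kel is assigned. They do not say which points enter the regression, and the R² limit does not name the interval it is computed on.

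A literal fit goes wrong in two opposing ways. Low concentrations during absorption flatten the fitted slope and lengthen t1/2. A steep distribution phase does the reverse. Kel, t1/2 and CL/F are listed endpoints. AUC0-inf is one of the three primary parameters (Protocol 8.2.3) and uses Kel twice: in its tail term, and through the rule that drops it when Kel is not assigned. If food delays absorption, such losses would fall mainly on the fed treatments B and D and leave the food and omeprazole comparisons of AUC0-inf with unequal data.

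**Working it through.** The documents give no numerical Kel, so there is no stated figure to reproduce. The textual conflict stands on the passages themselves. The calculation below only gauges its consequence.

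**Inputs from the documents**
- 19 post-dose times from 0.25 to 168 h (SAP 6.1) and LLOQ 1 ng/mL (SAP 6.2).
- R² limit 0.75 (SAP 6.5).
- LOXO-292 in patients is absorbed "with a time to maximum concentration (Tmax) of approximately 2 hours", with a half-life of at least 12 h (Protocol 8.1.1).

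**Assumed inputs**
- Half-life 12, 24 or 36 h; Tmax 2, 4, 6 or 8 h; Cmax 300, 1000 or 3000 ng/mL. That is 3 × 4 × 3 = 36 profiles.
- Each profile was run under one-compartment disposition and under biexponential disposition (70% of the intercept declining at 0.25/h). There was no noise and no lag.

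**Formulas**
- One compartment: C(t) ∝ exp(−Kel·t) − exp(−ka·t), with ka solved from Tmax = ln(ka/Kel)/(ka − Kel).
- t1/2 = 0.693/Kel; AUC0-inf = AUC0-t + Clast/Kel; CL/F = Dose/AUC0-inf.
- Fit (a): regression of ln C on t over all points above LLOQ. Fit (b): the last four quantifiable points.

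**Worked example: one compartment, true t1/2 36 h, Cmax 1000 ng/mL**

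| Tmax | Points at or before Tmax | All-points t1/2 | Ratio to 36 h | R² |
|---|---|---|---|---|
| 2 h | 6 of 19 | 37.96 h | 1.05 | 0.97 |
| 4 h | 9 of 19 | 42.17 h | 1.17 | 0.85 |
| 6 h | 10 of 19 | 47.45 h | 1.32 | 0.71 |
| 8 h | 11 of 19 | 53.84 h | 1.50 | 0.57 |

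Fit (b) returns 36.0 h in each case.

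**Whole grid, both models**

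| Tmax | All-points R² | All-points t1/2 ÷ terminal t1/2 | Profiles with R² < 0.75, per model |
|---|---|---|---|
| 2 h | 0.95-0.98 | 0.82-1.06 | 0 of 9 |
| 4 h | 0.80-0.96 | 0.96-1.17 | 0 of 9 |
| 6 h | 0.71-0.92 | 1.12-1.33 | 3 of 9 |
| 8 h | 0.57-0.87 | 1.28-1.55 | 4 of 9 |

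The terminal fit has R² of at least 0.995 throughout, so the 0.75 limit never removes a profile under the protocol's rule.

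**Effect on AUC0-inf.** The relative change is the extrapolated fraction times (t1/2 ratio − 1). With the terminal fit the extrapolated fraction is at most 4.1%. In the example at Tmax 8 h this is 0.041 × 0.495 = 2.0%; at Tmax 4 h it is 0.040 × 0.171 = 0.7%. Over all profiles the change runs from −0.6% to +2.0%. The upper end belongs to profiles that fail the R² limit; among those that pass, the range is −0.6% to +0.7%.

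**A second set of assumptions.** Twenty-one profiles were run: one-compartment with Tmax 2 h and half-life 12-30 h, and two-compartment with a 4 h distribution half-life and terminal half-life 20 or 30 h; Cmax was 100-2000 ng/mL. The terminal fit here used the best adjusted R² on at least 3 points after Cmax. All-points t1/2 ranged from +8% (13.0 vs 12.0 h) to −47% (15.7 vs 29.8 h) relative to the terminal fit. R² was 0.90-0.99 in every case, so the 0.75 limit would have flagged none of them. AUC0-inf moved by −2.5% to +0.1%.

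**The case against.** The strongest reply is that the SAP, read as a whole, already means a terminal fit. The row defines a terminal constant, SAP 6.5 withholds Kel when no terminal phase is apparent, the condition on Tmax makes most sense if at least 3 later points are fitted, and Table 14.2.1.9 prints an interval beside its R². On that reading the cell only says that BLQ values are ineligible, the section 8 statement is accurate, and the R² limit plainly refers to the printed interval. Any literal programming would also be visible in Table 14.2.1.9, with intervals starting at the first quantifiable sample.

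Much of this stands. Loose wording is the likeliest explanation, and nothing suggests a concealed change of method. The loss of AUC0-inf appears only at an assumed Tmax of 6-8 h. At the documented Tmax of about 2 h no profile is dropped, and the parameters compared in the ANOVA hardly move.

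It does not cure the cell. A profile with Tmax 2 h and a clear terminal decline meets every condition in SAP 6.5, and the stated method then says to use all quantifiable points. A programmer following Table 6.1 and one following the protocol could report different half-lives, each with a claim to be following the plan. An inference drawn from a table shell is a poor substitute for stating the rule.

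**Conclusion.** The concern holds. The Kel method in Table 6.1 is wrong as written: it conflicts with Protocol 13.3.2 and with the SAP's own interval, and section 8 does not acknowledge the difference. If followed literally, it distorts t1/2 by an amount and in a direction that depend on profile shape: 0.82-1.55 times the terminal value on the main grid, and down to about 0.53 on the second set. These ranges illustrate assumed noise-free profiles and are not bounds. With Tmax of 6-8 h it could also remove t1/2, CL/F and AUC0-inf through the R² limit. The documents give no fed Tmax, so a loss concentrated in treatments B and D is possible but not shown. AUC0-t and Cmax do not depend on Kel, and AUC0-inf changes little where it is retained. The point should be corrected, but it does not threaten the main comparisons.

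**What to change.** - **Table 6.1, Kel row:** replace the qualifier that admits every concentration above LLOQ with the protocol's rule, "using the maximum number of points in the terminal log-linear phase", with at least 3 quantifiable concentrations.
- **Same cell:** add that points up to and including Tmax are not used. This clarification goes beyond the protocol text and should be recognised as such.
- **SAP 6.5:** state that the R² limit of 0.75 applies to the interval reported in Table 14.2.1.9.

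The cost is one phrase and a clarifying sentence or two, with no extra data or analysis. If a fit to all quantifiable points really was intended, section 8 must list it as a change. Because AUC0-inf is a primary endpoint, Protocol 14.3 could then call for an amendment.
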